
 To describe the effect of tapinarof cream, 1% on psoriasis symptom severity and the associated impact on daily activities and attitudes in adults with plaque psoriasis 	
 Change in Peak Pruritus-Numeric Rating Scale (Peak Pruritus-NRS) from Baseline at Weeks 2, 4, 8, and 12 Change over time in psoriasis impact on daily activities, as measured by the Dermatology Life Quality Index (DLQI) total and individual dimension scores Change over time in psoriasis symptoms, as measured by the Psoriasis Symptom Diary (PSD) Change over time in physical component score and mental component score, as measured by the Short Form-36 (SF-36) questionnaire

 To evaluate the safety and tolerability of tapinarof cream, 1% 	
Safety:
 
 Incidence, frequency, and duration of treatment emergent adverse events (TEAEs) and serious adverse events (SAEs)

Objectives	Associated Endpoint
in adults with plaque psoriasis	
• Clinically significant change from Baseline in laboratory values• Clinically significant change from Baseline in vital signs• Mean Local Tolerability Scale (LTS) scores by visit

• To characterize the PK of tapinarof in adults with plaque psoriasis	Pharmacokinetic: 
• Plasma concentration of tapinarof at Weeks 4 and 12

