10.1. General Considerations

All study data will be summarized by treatment group using descriptive statistics. Categorical variables will be reported using frequency and percentage (eg, gender, race). Continuous variables will be reported using number of patients, mean, standard deviation (SD), median, minimum, and maximum. All efficacy and safety data will be listed by subject.

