10.4.3. Safety Analyses

The Safety Population will be used in the analysis of safety data. Data will be listed by subject and treatment and summarized by treatment. No formal statistical comparisons will be made for safety data.

The number and proportion of subjects with TEAEs will be summarized by treatment, system organ class, and preferred term for all TEAEs, all TEAEs considered by the Investigator to be related to study drug, all SAEs, and all TEAEs leading to study drug discontinuation. Summaries of AEs will be presented separately for double-blind and open-label treatment phases. All AE summaries will include information for AEs that occurred after administration of the first dose of study drug until completion of the final study visit. Data listings will be provided for subjects who discontinued the study due to an AE and for subjects with an SAE.

Selected laboratory data will be analyzed using descriptive summary statistics and will be presented by study visit and treatment group, including the number of non-missing observations, mean and SD, median, upper and lower quartiles, minimum and maximum for values and changes from Baseline. Categorical safety data will be analyzed using frequency tables and, if applicable, shift tables.

Vital signs will be listed by subject and summarized by visit.

Mean scores from the LTS will be summarized by visit.

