## 9. HANDLING OF MISSING DATA

### Imputation of Start and End Dates of Adverse Event (AE)

To calculate duration of Adverse Events, the following rules will be used where applicable to impute partial or completely missing start dates or end dates:

- If only the day is missing for a start date, the 1st of the month will be imputed. If the new estimated date falls before the date of first dose, while the known month and year match the month and year of the first dose, the date of first dose will be used as the new estimated date. The AE will be considered as a treatment-emergent AE (TEAE).
- If only the day is missing for an end date, the last day of the month will be imputed. If the new estimated date falls after the date of last study visit, the date of last study visit will be used as the new estimated date. Last study visit is defined as the Week 12 visit for those who elect to participate in the open-label long-term study, or the Week 16 Follow-up visit for those who fail to qualify for participation in the open-label study, or who qualify to participate but ultimately elect not to enroll.
- If both the day and the month are missing for a start date or end date, no imputation will be used, and the duration will not be calculated. However, if the year of start is the same or greater than the year of the first dose date, the AE will be considered as treatment emergent.

- If the start date or end date is completely missing, duration will not be calculated. However, an event with completely missing start date will be considered as treatment emergent.

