### **12.9.1 Adverse Events**

AE terms will be coded using the MedDRA dictionary. A treatment-emergent AE (TEAE) is defined as an AE that starts after the first dose of study medication. For subjects not rolling over to Open-label study, all reported AEs will be included in the Double-Blind phase summaries. For subjects rolling over to the Open-label study, all AEs with an onset date on or before the Week 12 visit date will be included in the Double-Blind phase summaries.

If relationship to treatment is missing, the event will be conservatively treated as related to study drug. Missing severity will be imputed to the highest severity level (most severe).

All AEs will be listed by treatment and by subject, detailing the verbatim term given by the investigator, the preferred term (PT), system organ class (SOC), onset date and time, end date and time, duration (days), CTCAE grade, outcome, relationship to study drug/treatment, action taken with study drug/treatment, other action taken to treat the event, seriousness and criteria for seriousness. Serious AEs (SAEs), TEAEs leading to study discontinuation, TEAEs related to study drug will also be listed separately. The following adverse event of special interest (AESIs) will be identified and listed separately: contact dermatitis, folliculitis, and headache.

AEs will be summarized by treatment and overall as incidence rates of:

- Any AE
- Any TEAE
- Any AESIs
- Any treatment-related TEAE, including definitely, probably, and possibly related
- Any TEAE leading to study drug discontinuation
- Any SAE (non-Fatal)
- Any serious TEAE
- Death
- Treatment-related Serious TEAE
- Serious TEAE leading to study drug discontinuation

Individual PTs will be summarized by treatment according to the following:

- All TEAEs by SOC in alphabetical order and PT in descending order of combined frequency (also for treatment-related TEAEs, TEAEs leading to study discontinuation and serious TEAEs)
- All TEAEs by SOC, PT, and maximum CTCAE grade
- All TEAEs by SOC, PT, and maximum causality (not related, related) to the study drug

In addition, TEAEs and serious TEAEs will be summarized by SOC (alphabetical order) and PT (descending order) for the following subgroups:

- Age (<65 and >= 65 years old)
- Sex
- Race (White, Other)

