At each level of summarization, a subject will be counted once if he/she reported one or more events. The severity of TEAEs and relationship to study drug will be summarized in a similar manner. For summaries of relationship to study drug, a subject will be classified according to the closest relationship. For summaries of TEAE CTCAE grade, a subject will be classified according to the worst grade.

For AESIs, summarization will be more extensive, reflecting the more detailed information collected. Information summarized will include number of events per subject, earliest onset day, duration (in days), causality, grade and seriousness of AESIs, outcome, actions taken with study drug, assorted physical characteristics of the AESIs, and demographic/baseline characteristics and PGA status of the subjects experiencing them. Each type of AESI will be summarized separately. If a subject has more than one treatment-emergent occurrence of an AESI, the subject's maximum duration, highest levels of causality and seriousness, maximum grade and generally the most extreme level of each characteristic will be summarized. If an AESI was ongoing at EOS, it will not be included in the duration summary.

A Kaplan-Meier figure will be generated for each AESI of time to first event. Subjects not experiencing the AESI will be censored at the date of study completion or discontinuation.

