## **13. CHANGES FROM THE PROTOCOL AND PLANNED ANALYSES**

The protocol specified change over time in physical component score and mental component score as measured by the SF-36 questionnaire as an exploratory endpoint. Scoring rules for the RAND 36-Item Health Survey (Version 1.0) are provided for the eight domain scores but not for the physical component score or the mental component score. Hence, summaries of the eight domain scores are planned.

No other changes from the protocol in planned analyses are noted. Any additional statistical analyses to handle modifications to study conduct and/or missing data due to the COVID-19 pandemic have been documented in Section 12.11 above in this SAP and will be finalized prior to database lock and unblinding of the study.

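### Duration of TEAEs and SAEs, and frequency if it means number of events, is a named safety endpoint with no planned by-arm summary outside the three AESIs

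*SAP*

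**What the plan says.** Protocol Section 2, like the synopsis, lists as the first safety endpoint: "Incidence, frequency, and duration of treatment emergent adverse events (TEAEs) and serious adverse events (SAEs". Frequency is not defined there.

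Protocol 10.4.3 sets out the adverse event analysis in terms of subjects: "The number and proportion of subjects with TEAEs will be summarized by treatment, system organ class, and preferred term for all TEAEs", and likewise for related TEAEs, SAEs and TEAEs that led to stopping study drug. It mentions neither event counts nor duration.

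SAP 12.9.1 follows the same line. The overview reads "AEs will be summarized by treatment and overall as incidence rates of", with rows that include any TEAE, any non-fatal SAE and any serious TEAE. The term-level tables begin with "All TEAEs by SOC in alphabetical order and PT in descending order of combined frequency", repeated for related TEAEs, serious TEAEs and TEAEs leading to study discontinuation. The counting rule is "At each level of summarization, a subject will be counted once if he/she reported one or more events".

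The same section plans a fuller summary for the AESIs, which covers how many events each affected subject had and how long they lasted. It uses the longest duration per subject and leaves out AESIs still ongoing at end of study. For every other adverse event, duration is one field in a listing by treatment and subject.

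SAP Section 9 gives date rules that apply to adverse events in general: "To calculate duration of Adverse Events, the following rules will be used where applicable". SAP Section 13 declares the SF-36 scoring change and then says "No other changes from the protocol in planned analyses are noted".

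**The concern.** An endpoint named in the protocol should have a result that the reader of the study report can compare between arms. Here the endpoint has three parts, and the planned tables clearly deliver only incidence. A subject with one brief event and a subject with several long ones contribute the same single count to each incidence table.

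What is at stake is the description of tolerability outside the three AESIs. If tapinarof did not change the share of subjects with an event but made events recur or persist, the incidence tables alone would not show it. The report would then have no by-arm duration figure for TEAEs or SAEs overall, although the protocol names duration as an endpoint.

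**Working it through.** The documents give no figure to reproduce on this point. The check sets the endpoint beside the planned outputs.

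| Endpoint part | Protocol 10.4.3 | SAP 12.9.1, TEAEs and SAEs overall | SAP 12.9.1, three AESIs |
|---|---|---|---|
| Incidence | By-arm subject counts and proportions | By-arm overview; SOC/PT tables for all TEAEs and serious TEAEs | Summarised |
| Frequency, as number of subjects | Same as incidence | Same as incidence | Summarised |
| Frequency, as number of events | Not planned | Not planned | Summarised |
| Duration | Not planned | Listing only | Summarised (longest per subject; ongoing events left out) |

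**Step 1: meaning of frequency.** Protocol 10.1 uses the word for category counts: "Categorical variables will be reported using frequency and percentage (eg, gender, race". SAP 12.9.1 orders preferred terms by combined frequency in tables that count each subject once. On that usage frequency is already covered. The endpoint nevertheless lists frequency as a separate item from incidence, which would be redundant if both meant subjects with an event. The documents do not settle the question.

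**Step 2: meaning of duration.** There is no second reading. Outside the AESIs, no by-arm duration summary appears in Protocol 10.4.3 or SAP 12.9.1. SAP 12.9 itself treats listing and summarising as two different things.

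**Step 3: what a subject count can hide.** Events per randomised subject = incidence × mean events per affected subject. At equal incidence the incidence cancels, and the ratio between arms equals the ratio of mean events per affected subject. The documents give no such means, so the following values are assumptions used only to show the range:

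- Incidence 20% in both arms, 1.1 events per affected subject in both: 0.20 × 1.1 = 0.22 in each arm; ratio 1.00.
- Incidence 20% in both arms, 1.8 on tapinarof and 1.1 on vehicle: 0.20 × 1.8 = 0.36 against 0.20 × 1.1 = 0.22; ratio 0.36 / 0.22 = 1.64.

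The incidence table is the same in both cases. This shows what the count leaves out; it does not predict the trial's data.

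**Step 4: are the data there?** Onset and end dates are collected, SAP Section 9 derives duration, and SAP 12.9.1 lists it. SAP Section 9 calculates no duration when an end date is wholly missing. An ongoing event would normally have no end date, so it would probably carry no duration value. Any summary therefore needs an explicit rule for ongoing events.

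**The case against.** Several points on the other side stand.

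- A reader might infer that the endpoint as a whole is not reported by arm. It is not so: incidence of TEAEs and SAEs is summarised by arm, and derived durations are listed by treatment and subject.
- A reader might infer that two of the three parts are missing. That depends on frequency meaning number of events. The documents more often use the word for counts of subjects or categories, so only duration is firmly missing.
- A reader might infer that the SAP dropped an endpoint and then denied it in Section 13. That section speaks of changes to planned analyses. Protocol 10.4.3 never planned event counts or a duration summary, so the SAP did not depart from that plan. The inconsistency lies first inside the protocol, between its endpoint list and its analysis section.
- The date rules in SAP Section 9 do not prove that a duration table for all TEAEs was intended. The listing field and the AESI summary are enough to explain them.
- Other by-arm tables could still reveal a difference: maximum CTCAE grade, causality, discontinuation, the AESI summaries, and local tolerability by visit. It would be wrong to say that more or longer events would be invisible everywhere.
- The protocol singles out the AESIs as clinically important, so putting the extra detail there is a reasonable choice.

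None of this supplies a by-arm duration result for TEAEs and SAEs overall. A listing for about 500 subjects is not a comparison of arms. That the protocol's own analysis section has the same gap explains its origin but does not close it.

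**Conclusion.** The point holds in limited form. The protocol names duration, and an undefined frequency, of TEAEs and SAEs as a safety endpoint. Protocol 10.4.3 and SAP 12.9.1 plan by-arm summaries of subject incidence only, apart from the three AESIs. One of the three parts (duration) lacks a by-arm summary on any reading. A second (frequency) lacks one only if it means number of events.

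The documents do not support the stronger charge of an undeclared deletion by the SAP, nor any estimate of how large a hidden difference might be; the ratio of 1.64 rests wholly on assumed inputs. Safety is descriptive here, with no formal comparison planned, and the primary efficacy conclusion is not affected. This is a minor reporting gap that is cheap to close before database lock.

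**What to change.** In SAP 12.9.1:

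1. Define frequency for this endpoint.
2. Show, by arm, the number of events beside the number of subjects in the overall table and in the SOC/PT tables for all, related and serious TEAEs.
3. Add a by-arm descriptive summary of duration for TEAEs and for serious TEAEs. State the unit (per event, or longest per subject) and report the number of events ongoing at end of study, so that they are not silently dropped. Simple descriptive statistics are enough. A Kaplan-Meier median pooled over all TEAEs is not needed and would mix unlike and repeated events.

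Reconcile the endpoint wording in the protocol synopsis and Section 2 with Protocol 10.4.3, or record in SAP Section 13 how the endpoint has been interpreted. A note on its own would tidy the record but would still leave duration without a by-arm result.

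The cost is one extra column in tables already planned and one extra table, from dates already collected and a duration already derived. It needs no new data and no added hypothesis test.

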3.2. Treatment Groups and Duration

This 12-week, Phase 3 study is a double-blind, vehicle-controlled treatment study in which subjects will be randomized in a 2:1 ratio to receive once daily treatment with either tapinarof cream, 1% or matching vehicle cream.

At the conclusion of the 12 weeks of treatment in this study, subjects will have the option to enroll in a separate Phase 3 open-label long-term safety and efficacy study of 40 weeks in duration. Details of that study are provided in a separate clinical trial protocol.

A subject will be considered to have completed this study when he/she completes all required procedures/visits for the 12-week double-blind treatment phase.

The end of study is defined as when the last active subject has completed the Week 16 Follow-up Visit 4 weeks after the end of treatment (if subject does not enroll in the separate long-term study) OR the last active subject has completed the 12 weeks of treatment in this study (if subject enrolls in the separate long-term study).

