8.3.2. Follow-Up of Adverse Events

After the initial AE/SAE report, the Investigator is required to proactively follow each subject at subsequent visits/contacts. All SAEs and nonserious AEs will be followed until resolution, until the condition stabilizes, until the event is otherwise explained, or until the subject is lost to follow-up.

The Investigator will assess the outcome of each AE using the following criteria:

- **Recovered/Resolved:** The event has improved or subject recuperated.
- **Recovered/Resolved with sequelae:** The subject has recuperated but retained pathological conditions resulting from the prior disease or injury.
- **Recovering/Resolving:** The event is improving.
- **Not recovered/Not resolved:** The event has not improved or subject recuperated.
- **Unknown:** The outcome of the event is not known, not observed, not recorded, or refused.
- **Fatal:** Termination of life as an outcome of the AE.

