## 12. STATISTICAL EVALUATION

### 12.1 Subject Disposition

The number and percentage of subjects screened, screen failed along with reason for screen failures, randomized, included in each analysis population, completing 12-Week Double-Blind treatment, completing the study, withdrawing from treatment (together with the reasons for withdrawal), withdrawing from the study (together with the reasons for withdrawal), and subjects

excluded from PP population (together with the reasons for exclusion) will be summarized using frequencies and percentages by treatment group. For subjects who have completed the 12-Week treatment, the number and percentage of those who elect to enroll in the open-label study will be summarized.

Enrollment and disposition will be listed by subject. Screen failures and subjects not randomized will also be listed by subject.

The number of days in the study (date of study completion / discontinuation minus date of Day 1 plus 1) will be summarized descriptively by treatment group.

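### Leaving AESIs that are ongoing at EOS out of the duration summary makes AESI durations lean short, and EOS itself is not pinned down

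*SAP*

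**What the plan says.** SAP section 12.9.1 gives each AESI type its own summary, including duration in days and outcome. For a subject with several occurrences, the subject's "maximum duration, highest levels of causality and seriousness, maximum grade and generally the most extreme level of each characteristic will be summarized". The next sentence makes an exception: "If an AESI was ongoing at EOS, it will not be included in the duration summary".

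SAP section 9 has the same effect on an event with no end date: "If the start date or end date is completely missing, duration will not be calculated".

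The only AESI display that handles censoring is a Kaplan-Meier figure of time to first event. It concerns onset, not duration: "Subjects not experiencing the AESI will be censored at the date of study completion or discontinuation".

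On follow-up, protocol section 8.3.2 states: "All SAEs and nonserious AEs will be followed until resolution, until the condition stabilizes", or until the event is otherwise explained or the subject is lost to follow-up. Duration of treatment-emergent events is a listed safety endpoint (protocol synopsis and section 2), and protocol section 8.1.3 asks sites to collect the duration of each AESI. SAP section 12.9 plans no formal comparison of safety data.

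**The concern.** An event enters the duration summary only if it ends before observation ends. This is right truncation: the longer an episode lasts and the later it starts, the more likely it is to be left out. The direction does not depend on how long the events actually last.

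Three features add to the problem.

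- **Against the neighbouring rule.** The preceding sentence takes the most extreme value per subject. The exception does not say whether it removes the event or the subject. If the event (the natural reading), a shorter resolved episode can become the subject's reported maximum. If the subject, that subject drops out of the summary.
- **Undefined cut-off.** The SAP abbreviation list expands EOS only as end of study. Protocol sections 3.2 and 7.6 define that for the whole trial, by the last active subject. SAP section 9 instead defines a last study visit per subject (Week 12 for those who roll over, otherwise Week 16), and sections 12.1 and 12.9.1 use each subject's completion or discontinuation date. Even that date is open for subjects who do not roll over. The protocol says "A subject will be considered to have completed this study when he/she completes all required procedures/visits for the 12-week double-blind treatment phase", while the SAP says "For subjects not rolling over to Open-label study, all reported AEs will be included in the Double-Blind phase summaries", which reaches into the follow-up period.
- **Roll-over subjects.** Their events count with onset up to the Week 12 visit, which is also their last study visit. A late AESI has almost no time to resolve on study.

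At stake is a descriptive figure for a named safety endpoint, on events that the protocol singles out as clinically important.

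**Working it through.** The plan states no AESI duration or proportion ongoing, so there is no figure to reproduce. The calculation below only illustrates size.

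**From the documents.** The target days are Day 85 (Week 12) and Day 113 (Week 16) in SAP section 11.4, so observation ends F = 84 or F = 112 days after Day 1.

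**Assumed.** One event per subject, onset uniform over 84 days, and exponential duration with mean m of 3, 7 or 28 days. EOS is read per subject, and nothing is recorded after F.

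**Formulas.** The time left after onset, L, is uniform between F − 84 and F. An event is kept only if its duration is at most L.

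- Share dropped: q = (m/84) × [exp(−(F−84)/m) − exp(−F/m)]
- A = (m/84) × [(F−84+m) exp(−(F−84)/m) − (F+m) exp(−F/m)]
- Mean of the resolved events: (m − m·q − A) / (1 − q)

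**m = 7, F = 84.** q = (7/84)(1 − e⁻¹²) = 0.083. A = (7/84)(7 − 91e⁻¹²) = 0.583. Mean = (7 − 0.583 − 0.583)/0.917 = 6.4.

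**m = 28, F = 84.** q = (28/84)(1 − e⁻³) = 0.317. A = (28/84)(28 − 112e⁻³) = 7.475. Mean = (28 − 8.869 − 7.475)/0.683 = 17.1.

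| True mean (days) | Dropped, to Week 12 | Reported mean | Dropped, to Week 16 | Reported mean |
|---|---|---|---|---|
| 3 | 3.6% | 2.9 | <0.1% | 3.0 |
| 7 | 8.3% | 6.4 | 0.2% | 6.9 |
| 28 | 31.7% | 17.1 | 11.7% | 21.2 |

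**Repeat episodes (simulation, to Week 12).** Assume that 30% of subjects whose first episode resolves by Day 84 have a second, with onset uniform over the time left.

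- The mean of subject maxima (true / event-level exclusion / subject-level exclusion) is 8.0 / 6.9 / 6.9 at m = 7 and 31.5 / 17.6 / 17.4 at m = 28.
- The two readings differ mainly in how many affected subjects are lost: 8% (event level) against 16% (subject level) at m = 7, and 32% against 44% at m = 28.
- With recurrence from 10% to 50% and event-level exclusion, 1.0% to 4.9% of affected subjects (m = 7) or 1.5% to 7.3% (m = 28) have an ongoing episode already longer than their reported maximum.

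**Does censoring repair it? (simulation, single events)**

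- Current rule, to Week 12: median 4.4 against a true 4.9 (m = 7), and 12.8 against 19.4 (m = 28).
- Kaplan-Meier with one cut-off for all events: 4.9 and 19.4, so the truth is recovered.
- Kaplan-Meier with unresolved events censored at Day 84 but later resolution dates counted, m = 28, assuming 14 or 28 days of further follow-up: median 17.9 or 18.4, and upper quartile about 34 against a true 38.8. This censoring depends on the outcome and brings back part of the bias. At m = 7 the effect is negligible.
- Kaplan-Meier with censoring at the actual last follow-up, m = 28: median 19.4 and upper quartile 38.8.

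**The case against.** The strongest reply is that the exclusion is openly declared and its effect can be seen. AESI outcome is summarized in the same set of displays, AESIs are listed separately, and the adverse-event listing gives dates, duration and outcome. A reader can count the unresolved events, and no test or decision rests on the duration line. This stands, and it is why the point is minor. It does not correct the statistic.

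Second, sites follow events until they resolve or stabilize, and under the protocol's trial-level definition of end of study fewer events would count as ongoing. Both would shrink the effect, and the illustration, which stops at Day 84 or Day 112, models neither. This also stands. However, the documents do not say whether a resolution after a subject's last visit, in particular after roll-over, is recorded in this study's database. On a subject-level reading the sentence excludes an event that was ongoing at EOS even if its later end date is known.

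Third, nothing in the documents supports a 28-day mean. That is correct: it shows when the rule would matter and is not a forecast.

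A reader might go further and infer that the rule flatters tapinarof against vehicle, or that unresolved events are concealed. The documents support neither. The rule applies to both arms, no arm-specific durations or roll-over rates are given, and the unresolved events remain in the incidence, outcome and listing displays.

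**Conclusion.** The concern holds as a minor point about one descriptive summary. The duration summary leans short because it leaves out unresolved AESIs, and no other part of the plan corrects it. Under the stated assumptions and observation to Week 12, the mean is short by 0.1 to 0.6 day for true means of 3 to 7 days, and by about 11 days for a true mean of 28. Observation to Week 16 makes the loss close to nil at 3 to 7 days and about 7 days at 28. The actual size in this trial cannot be derived from the documents. Separately, EOS needs a definition and the exclusion needs a unit (event or subject). Incidence, severity, the efficacy results and type I error are not affected.

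**What to change.** Replace the exclusion sentence in SAP section 12.9.1 with:

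> For each AESI type and treatment group, the number and percentage of subjects with an AESI not resolved at their last AE follow-up in this study will be shown beside the duration summary. Duration will be summarized with the Kaplan-Meier median and quartiles, using each subject's longest observed or censored episode. An unresolved AESI will be right-censored at the date its status was last assessed in this study, and the same follow-up cut-off will apply to resolved and unresolved events.

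If a fixed cut-off is preferred (Week 12 visit for roll-over subjects, Week 16 or last contact otherwise), resolution dates after it must not be counted as events.

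Two additions are needed.

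- In the SAP section 9 rule on missing end dates, make an exception for unresolved AESIs. Otherwise that rule still removes them. An AESI recorded as resolved but with no end date can stay under the present rule.
- State how AESIs with outcome *Unknown* or *Fatal* (protocol section 8.3.2) are handled.

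**Cost.** The SAP wording changes and one more table for each of the three AESIs. Durations may look less favourable. Kaplan-Meier assumes non-informative censoring, which is weaker for subjects who withdraw because of the AESI. Taking the longest observed or censored episode leaves a small low bias: in the Week 12 simulation with 50% recurrence, the median is low by 0.2 day at a true mean of 7 and by about 2 days at 28. With few events in an arm, the upper quartile may not be reached.
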